4. STATISTICAL ANALYSES

The analyses described in this SAP will supersede those specified in the Protocol Version 3, 7 March 2023 or thereafter.

4.1 GENERAL CONSIDERATIONS

The primary analysis will take place when all study participants have completed their last study treatment administration in the Treatment Cross-over Period. Summaries of secondary study endpoints, including PK and ADA measurements, participant-reported TASQ and EORTC QLQ-C30 responses, selection of treatment administration method for the Treatment Continuation Period, HCP reported HCPQ responses, and safety endpoints will be included in the primary analysis, based on all data up to the clinical cut-off date.

The final study analysis that includes all secondary endpoints including all questionnaires, PK, ADA, and safety endpoints will be conducted after the end of the study (i.e., when all patients have received 16 cycles of atezolizumab or discontinued study treatment).

Summaries of participants' preference, analysis of PROs, including the primary endpoint, HCP reported outcomes and clinical benefit, as well as sensitivity analysis for preference and satisfaction, will be based on the FAS, according to the treatment sequence assigned.

All safety analyses will be performed in the safety-evaluable population, unless otherwise specified. Participants will be analyzed according to the treatment they actually received. In case of protocol deviations leading to a treatment sequence with more than one treatment switch, participants will be analyzed according to the treatment sequence assigned.

Continuous variables will be summarized by the mean, standard deviation, median and range (minimum and maximum). Categorical variables will be summarized by number/percentage of participants.

Unless otherwise stated, baseline values are the last available data obtained prior to the patient receiving the first dose of study treatment (or at screening, for patients who were not treated).

4.2 PRIMARY OBJECTIVE

Analysis will be done for all patients and, as a part of exploratory analysis when applicable, separately among participants with early-stage NSCLC and chemotherapy-naive participants with Stage IV NSCLC.

The primary objective of this study is to evaluate participant preference for atezolizumab SC based on the proportion of participants indicating an overall preference for atezolizumab SC compared with atezolizumab IV in Question 1 of the PPQ. Question 1 of the PPQ is as follows: "All things considered, which route of administration did you prefer?".

4.2.1 Definition of Primary Estimand

The evaluation of participant preference for atezolizumab SC compared with atezolizumab IV will be analyzed as defined in [Table 1](#) of Section [1.1](#) of the SAP.

4.2.2 Main Analytical Approach for Primary Estimand

Patient preference will be summarized and presented by overall and by randomized treatment sequence using FAS. As stated in [Table 1](#), for intercurrent events such as patients who died, early discontinued from treatment or never received any study treatment, as well as patients lost to follow-up prior to providing an answer to Question 1 of the PPQ will be excluded from the analysis. Responses to Question 1 of the PPQ collected before at least two consecutive administrations of treatment, with each treatment administration route, were received by the patient will not be included in the analysis.

Patient preference will be summarized by presenting the number and proportion of patients in each category (SC, IV and No preference). A point estimate with associated exact Clopper-Pearson binomial 95% CI for the proportion of patients who preferred atezolizumab SC will be calculated and will be displayed by randomized treatment sequence and overall.

4.2.3 Supplementary Estimand

An analysis will be done for the evaluation of participant preference for atezolizumab SC compared with atezolizumab IV based on the FAS. All the attributes are similar to the primary estimand except the variable attribute where now patients who discontinued earlier to the study treatment but received at least one dose of each treatment route will be analyzed (cf. [Table 1](#)). Patients who died, never received any treatment or are lost to follow-up prior to providing an answer to Question 1 of the PPQ will be excluded from the analysis.

4.2.4 Subgroup Analyses for the Primary Objective

As a part of exploratory analysis, patient preference will also be summarized by presenting the number and proportion of patients in each category (SC, IV and No preference) by stratification factors: disease stage (II, III, IV) and type of surgery (no surgery, pneumonectomy, any other lung surgery) according to [Table 1](#).

4.2.5 Secondary Endpoints Analyses

4.2.6 Patient responses to questions of the TASQ-SC and TASQ-IV

The TASQ is a 12-item questionnaire measuring the impact of the mode of treatment administration on five domains: Physical Impact, Psychological Impact, Impact on Activities of Daily Living, Convenience, and Satisfaction. The Physical Impact domain comprises of 3 items (Q2: Pain experience, Q3: Swelling experience, Q4: Redness experience), the Psychological Impact domain contains one item (Q5: Feeling restricted by SC injection/IV infusion), The Impact on Activities of Daily Living contains one item (Q8: Lost/gained time), The Convenience domain contains 2 items (Q6: Is it convenient to get SC injection/IV infusion, Q7: Bothered by the amount of time to get SC injection/IV infusion), and the Satisfaction domain includes 2 items (Q1: How satisfied or dissatisfied are you with the SC injection/IV infusion, Q12: Would you recommend the way you received the treatment). All 9 TASQ items included in the above domains have five response options:

- Reverse-coded response values will be created for eight of the TASQ items (Q1, Q2, Q3, Q4, Q5, Q6, Q7 and Q12)

In addition, there are three questions in the TASQ (Q9, Q10, Q11) that are not part of the above domains. These three questions will be analyzed separately and presented descriptively.

Participant assessed satisfaction with atezolizumab SC and atezolizumab IV will be based on participant responses to Question 1 of the TASQ-SC and TASQ-IV respectively.

The patient satisfaction will be described by randomized treatment sequence and overall, as a categorical variable with the number and proportion of patient responses to each modality of the question (very satisfied, satisfied, ..., very dissatisfied).

In addition, responses of the TASQ-SC and TASQ-IV will be summarized by domain (physical impact, psychological impact, impact on activities of daily living, convenience, and satisfaction).

For the three domains that contain more than one item (Physical Impact, Convenience and Satisfaction), the algorithm will be the following:

If there are no missing responses, the domain will be scored using the formula:

$$Domain\ Score = \frac{\left[\frac{Sum\ of\ completed\ item\ response}{Number\ of\ completed\ items} - 1 \right] \times 100}{Max\ possible\ item\ response\ value - Min\ possible\ item\ response\ value}$$

However, if there are any missing responses within a domain then the domain will not be scored (i.e., a missing value is assigned to the domain).

Since the maximum possible item response value is 5 and the minimum possible response value is 1 for all TASQ items, a simpler way to represent the above formula for the TASQ domains is:

$$TASQ\ Domain\ Score = [\text{Mean of completed item responses} - 1] \times 25$$

Descriptive statistics will be computed for these three domains by randomized treatment sequence and overall.

The two domains that contain only one item (Psychological Impact and Impact on Activities of Daily Living) will be described by randomized treatment sequence and overall, in the same way as the patient satisfaction in Question 1: first as a categorical variable with the number and proportion of patient responses to each modality of the question, and secondly as a continuous variable with descriptive statistics.

The three descriptive questions (Q9, Q10, Q11) that are not part of the above domains will be summarized individually by the number and proportion of patient responses to each modality of the question.

The proportion of responses will be based on the number of patients who answered the respective question. All TASQ analyses will be performed on the FAS. The analysis will be done for all patients and as an exploratory analysis, as applicable, separately among participants with early-stage NSCLC and chemotherapy-naive participants with Stage IV NSCLC.

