3.3.4 Rationale for Randomized Cross-Over Design

The primary objective of this study is to assess participant-reported preference for atezolizumab SC compared with atezolizumab IV. Participants will be randomized to receive either atezolizumab SC for three treatment cycles followed by atezolizumab IV for three treatment cycles versus receiving atezolizumab IV first, followed by atezolizumab SC. Participants in both treatment groups will then choose either IV or SC administered atezolizumab for their remaining treatment cycles.

Randomization accommodates potential treatment sequencing-related differences such as in the nature and/or frequency of infusion-related reactions (IRRs) with either administration route (e.g., if IRRs to IV formulation occur more frequently in the early cycles of dosing) or in adverse events attributable to switching administration routes. At the same time, the cross-over design provides exposure to both study regimens allowing each participant to act as their own control for PROs measured after atezolizumab Cycle 3 and atezolizumab Cycle 6.

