6.5 SECONDARY ENDPOINT ANALYSES

Participant assessed satisfaction with atezolizumab SC and atezolizumab IV will be based on participant responses to Question 1 of the TASQ-SC and TASQ-IV respectively. In addition, responses of the TASQ-SC and TASQ-IV will be summarized by domain (physical impact, psychological impact, impact on activities of daily living, convenience and satisfaction).

The proportion of participants who select each treatment administration route for the Treatment Continuation Period will be summarized for all participants who complete the Treatment Cross-over Period.

EORTC QLQ-C30 scores including change from baseline, will be summarized by treatment arm and by time.

Healthcare professional perception of time/resource use and convenience with atezolizumab SC will be assessed by summarizing responses to individual questions of the HCPQs.

The percentage of participants with continuing clinical benefit after 16 cycles of atezolizumab will be summarized (stratified by disease stage at study entry).

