Appendix 1: Schedule of Activities

- q All women of childbearing potential will have a serum pregnancy test at screening, within 14 days prior to initiation of study treatment. Urine pregnancy tests (or serum, if urine is not feasible) will be performed at specified subsequent visits during treatment, at the treatment discontinuation visit, and may be required beyond treatment discontinuation, monthly for 5 months after the final dose of atezolizumab. Pregnancy tests after study treatment discontinuation can be performed at home. If a urine pregnancy test is positive, it must be confirmed by a serum pregnancy test.
- r In accordance with country-specific health authority mandates, pregnancy tests may be required beyond treatment discontinuation, monthly for 5 months after the final dose of atezolizumab. Pregnancy tests after study treatment discontinuation can be performed at home. If a home urine pregnancy test is positive, it must be confirmed by a serum pregnancy test and if confirmed, immediately communicated to the treating physician.
- s TSH, free T3 (or total T3 for sites where free T3 is not performed), and free T4 will be assessed on Day 1 of Cycle 1 and every four cycles thereafter (i.e., Cycles 5, 9, 13, etc.).
- t At screening, participants will be tested for HIV, HBsAg, HBsAb, total HBcAb, and HCV antibody. If a participant has negative HBsAg and HBsAb tests and a positive total HBcAb test at screening, an HBV DNA test must also be performed. If a participant has a positive HCV antibody test at screening, an HCV RNA test must also be performed.
- u Urinalysis includes pH, specific gravity, glucose, protein, ketones, and blood; dipstick permitted.
- v Urinalysis should be performed as clinically indicated during study treatment.
- w The Patient Preference Questionnaire (PPQ) must be completed following study treatment administration on Day 1 of Cycle 6 of the Treatment Cross-over Period. Participants who discontinued study treatment prior to study treatment Cycle 6 should complete the questionnaire at the time of discontinuation as long as they have received at least one dose of atezolizumab SC and atezolizumab IV post-randomization.

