- x Participants in Arm A will complete the Therapy Administration Satisfaction Questionnaire for SC administration (TASQ-SC) immediately following study treatment administration on Day 1 of Cycle 3 of the Treatment Cross-over Period and the Therapy Administration Satisfaction Questionnaire for IV administration (TASQ-IV) immediately following study treatment administration on Day 1 of Cycle 6 of the Treatment Cross-over Period. Participants in Arm B will complete the TASQ-IV and TASQ-SC immediately following study treatment administration on Day 1 of Cycle 3 and 6 of the Treatment Cross-over Period, respectively.
- y During the study treatment periods, participants must complete the EORTC QLQ-30 and EQ-5D-5L before the participant and clinician receives any information on disease status and prior to treatment administration on the scheduled visit day. EORTC QLQ-C30 and EQ-5D will be administered at Cycle 7, 10, 13, and 16 of the Treatment Continuation Period.
- z Each Healthcare Professional Questionnaire (HCPQ) will be completed by the applicable HCP after each study treatment preparation and/or administration for each participant. Applicable HCPs are described in each of the questionnaires (HCPQ-Treatment Room, HCPQ-Drug

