4.2.8 EORTC QLQ-C30

EORTC data will be analyzed based on the FAS, unless specified otherwise.

Summary statistics (mean, standard deviation, median, and range) of linearly transformed absolute scores and mean changes from baseline will be calculated for all

items and subscales (treatment-related symptoms and function, Global Health Status/HRQoL) of the EORTC QLQ-C30 at each assessment timepoint for each randomized treatment arm.

The EORTC QLQ-C30 data will be scored according to the EORTC scoring manual (Fayers et al. 2001). Missing data will be reported by timepoint. In the event of incomplete data, for all questionnaire subscales, if more than 50% of the constituent items are completed, a pro-rated score will be computed consistent with the scoring manuals and published validation reports. For subscales with less than 50% of the items completed, the subscale will be considered as missing. PRO completion, compliance rates, and reasons for missing data will be summarized at each timepoint by randomized treatment arm on the FAS.

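### TASQ satisfaction with SC and with IV is tabulated separately, with no within-participant comparison, although own-control PROs justify the cross-over

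*SAP*

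**What the plan says.** **TASQ.** Protocol 3.3.4 gives a reason for the cross-over: it exposes everyone to both regimens, "allowing each participant to act as their own control for PROs measured after atezolizumab Cycle 3 and atezolizumab Cycle 6". Footnote x of Protocol Appendix 1 schedules one form per route. Arm A completes TASQ-SC at Cycle 3 and TASQ-IV at Cycle 6, and for the other arm "Participants in Arm B will complete the TASQ-IV and TASQ-SC immediately following study treatment administration on Day 1 of Cycle 3 and 6". SAP 4.2.6 then plans: "The patient satisfaction will be described by randomized treatment sequence and overall, as a categorical variable". Domain scores are summarised in the same layout. On denominators it says "The proportion of responses will be based on the number of patients who answered the respective question". SAP 4.1 lists the summaries to be produced, "as well as sensitivity analysis for preference and satisfaction, will be based on the FAS". For preference, SAP 4.2.3 supplies a supplementary estimand; for satisfaction, no section defines anything.

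**Early stopping.** The PPQ has a rule in footnote w of Protocol Appendix 1: "Participants who discontinued study treatment prior to study treatment Cycle 6 should complete the questionnaire at the time of discontinuation", provided at least one dose of each route has been given. The TASQ footnote has no such rule.

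**QLQ-C30.** The objective in SAP Table 2 is quality of life with SC and with IV. SAP 4.2.8 plans summaries "of the EORTC QLQ-C30 at each assessment timepoint for each randomized treatment arm", and Protocol 6.5 likewise: "EORTC QLQ-C30 scores including change from baseline, will be summarized by treatment arm and by time". From Cycle 7 the participant chooses the route (Protocol 3.1.1).

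**The concern.** A two-period cross-over yields, for each participant, a pair of satisfaction ratings. The quantity it measures well is the within-person difference. SAP 4.2.6 reports the two margins and leaves the pairing unused. Margins describe satisfaction with each route. They do not say how many people rated SC higher, IV higher or both alike, and they give no standard error for the difference.

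Because the TASQ is tied to Cycles 3 and 6, a participant who stops after Cycle 3, 4 or 5 has only the first-route form. The overall SC and IV columns can therefore contain different people and a different mix of sequences.

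For QLQ-C30, arm plus cycle identifies the route until participants choose it (apart from deviations, or a move to IV after SC toxicity under Protocol 4.3.2.1). After that, a by-arm column is a blend of routes, and no planned table describes quality of life by route.

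**Working it through.** **1. The plan's own figure.** SAP 2.2 assumes 70% preferring SC, a half-width of 8 points and 28% not evaluable.
- n = 1.96² × 0.70 × 0.30 / 0.08² = 126.05, stated as 126.
- 126 / (1 − 0.28) = 175, as stated, so 175 − 126 = 49 planned losses.

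Both figures reproduce. They describe PPQ evaluability.

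**2. Who holds which form** (Protocol Appendix 1; SAP Table 1, which requires two consecutive doses of each route for the primary estimand and one for the supplementary). The table assumes each scheduled form is completed.

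| Last cycle treated | TASQ forms | PPQ due | In primary PPQ analysis |
|---|---|---|---|
| 3 | first route only | no | no |
| 4 | first route only | yes | no (supplementary only) |
| 5 | first route only | yes | yes |
| 6 or later | both | yes | yes |

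The Cycle 5 row matters: such a participant can be among the 126 without being a TASQ pair.

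**3. Unpaired share of an overall column.** Take equal arms, everyone completing the first form, and a fraction f lacking the second. The SC column holds N/2 from Arm A and (1 − f)N/2 from Arm B; fN/2 of the Arm A entries have no counterpart. The share is f/(2 − f), and the IV column mirrors it.
- No losses between forms: 0%.
- All 49 lost between forms: f = 0.28, share = 24.5/150.5 = 16.3%. Arm A then supplies 87.5/150.5 = 58.1% of the SC column but 63/150.5 = 41.9% of the IV column.
- If, in addition, 10 of the 126 stopped after Cycle 5 (assumption): f = 59/175, share = 29.5/145.5 = 20.3%.

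With equal losses in both arms the sequence mix differs between columns but the period mix does not. With unequal losses the period mix differs too.

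**4. What the margins leave open.** Illustration only: the satisfaction rates are assumed, and 126 pairs is a planning figure that pairing can fall below. Let b be the share satisfied with SC only and c the share satisfied with IV only. The margins fix b − c and nothing more. Half-width = 1.96 × √[(b + c − (b − c)²)/126].

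| Assumed SC / IV satisfied | b | c | 95% half-width, points |
|---|---|---|---|
| 85% / 75% | 0.10 to 0.25 | 0 to 0.15 | 5.2 to 10.9 |
| 90% / 80% | 0.10 to 0.20 | 0 to 0.10 | 5.2 to 9.4 |
| 80% / 60% | 0.20 to 0.40 | 0 to 0.20 | 7.0 to 13.1 |

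In the first row, identical published tables fit anything from 13 to 32 people satisfied with SC only (12.6 to 31.5) and 0 to 19 with IV only (0 to 18.9).

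**5. Why average over sequences.** Let τ be the SC minus IV effect and π an additive change from Cycle 3 to Cycle 6. The within-person SC minus IV mean is τ − π in Arm A and τ + π in Arm B. Their simple average is τ, even when the two arms contribute different numbers of pairs.

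**6. QLQ-C30.** Post-baseline timepoints are Cycles 3, 6, 7, 10, 13, 16 and end of treatment: 7. The form is completed before dosing (Protocol Appendix 1, footnote y), so Cycle 7 still reflects the Cycle 4–6 route. In participants treated past Cycle 6, the other four (Cycles 10, 13, 16 and end of treatment) follow a self-chosen dose. If shares pA and pB of the arms choose SC, the arm contrast carries only pA − pB of a constant route difference: 0 at 70%/70%, 0.2 in absolute size at 60%/80%, 0.4 at 50%/90% (all assumed).

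**The case against.** The strongest reply is that the TASQ objective is worded as satisfaction with each route, not as a comparison, and two descriptive tables answer it. The trial's comparative question belongs to the PPQ, which is itself a within-participant judgement, and SAP 2.1 plans no hypothesis test even there. This stands as a limit on weight: the plan does not fail its stated objective. It does not answer the gap between Protocol 3.3.4 and the analysis, or the undefined sensitivity analysis in SAP 4.1.

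Two further points are fair. TASQ Question 11 asks each person which route they would prefer, so the TASQ contains a within-person item; but it records preference, and at Cycle 3 only one trial route has been experienced. SAP 4.2.6 also implies that Question 1 will be summarised as a continuous score, so route means can be compared within a sequence. That gives a difference of means among possibly different respondents, still without its standard error.

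On QLQ-C30, by-arm tables preserve randomization, while by-route tables are self-selected. The form is completed before dosing and mostly recalls the past week, so on a 21-day cycle it is a weak measure of an administration effect. This stands, and is why the point is secondary.

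A reader might take 126 as the number of TASQ pairs and 16.3% as the largest possible unpaired share. The documents do not support that: both figures come from PPQ evaluability, and step 2 shows the two can part.

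**Conclusion.** The point holds as a low-cost improvement to secondary, descriptive analyses. The pairs are scheduled, the design is justified by them, and the SAP neither compares them nor defines the satisfaction sensitivity analysis it names. SAP 4.2.7 already cross-tabulates PPQ Question 1 against the continuation choice among those with both answers, so the kind of table is familiar to the plan.

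The size depends on how many participants stop between Cycles 3 and 6, which the documents do not give. The unpaired share is 0% with no such losses, 16.3% if all 49 planned PPQ losses fall there, and more if some PPQ-evaluable participants stop after Cycle 5. The half-widths show that the margins leave the answer open; they do not forecast precision.

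A reader might infer that the primary preference estimate or the sample size is in doubt. Neither is: the PPQ is answered within participant, and both planning figures reproduce. A reader might also infer that the by-arm QLQ-C30 tables are wrong. They are valid by-arm summaries that no longer separate the routes from Cycle 10. Nor does the argument extend to PK: SAP 4.4.3 leaves that display flexible, and samples up to predose Cycle 6 follow an assigned route and serve the exploratory objective.

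**What to change.** **SAP 4.2.6.** Keep the planned tables. Among participants with both forms, add:
- a TASQ-SC by TASQ-IV cross-tabulation of Question 1;
- the within-participant SC minus IV difference with 95% CI for Question 1 (reverse-coded value) and the domain scores, as the simple average of the two sequence-specific means, with standard error ½√(s²A/nA + s²B/nB);
- the number with one form only, by sequence and reason, including a move to IV after SC toxicity.

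State in SAP 4.1 that this is the satisfaction sensitivity analysis.

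**SAP 4.2.8 (lesser).** Keep the by-arm tables. For participants treated past Cycle 6, add descriptive summaries at Cycles 10, 13, 16 and end of treatment by route of the most recent dose, labelled non-randomized and self-selected. Flag anyone who changes route during continuation. Keep the predose Cycle 7 form with the Cycle 4–6 route.

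**Cost.** SAP wording and a few tables; no new data and no change to N. The paired result applies only to participants who completed both forms. The less-chosen route may be small: if 70% of 126 chose SC (assumption), about 88 would be on SC and 38 on IV.
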